#### B. Source of subjects and recruitment methods

This study will be registered with ClinicalTrials.gov prior to the recruitment and enrollment of human subjects. All participants will be recruited from BHCHP clinical sites. BHCHP does not have its own IRB but instead will rely on the Mass General Brigham Human Research Committee for IRB review through a reliance agreement initiated through SMART IRB. In addition to being a faculty physician-investigator at Massachusetts General Hospital and Harvard Medical School, the study PI has over 20 years of clinical experience with homeless patients and more than 13 years of research experience relating to the health of homeless people. He has been a staff physician at BHCHP since 2008 and was named the Director of Research at BHCHP in 2017.

Recruitment of study participants will occur at up to 3 venues; however, initial efforts will focus on the first of these sites:

*a) Medical center venue:* Jean Yawkey Place, adjacent to Boston Medical Center, is the BHCHP headquarters facility where medical, behavioral health, and dental clinics operate 5 days per week with an on-site pharmacy and medical respite unit. Compared to other BHCHP locations, Jean Yawkey Place has the highest volume of patients, the most space, and the greatest flexibility in space configuration. This will allow study personnel to conduct in-person participant recruitment while practicing COVID-appropriate social distancing and prioritizing the health and well-being of both participants and study staff.

Depending on the status of the COVID-19 pandemic, recruitment may later expand to two additional locations when safe to do so:

- b) Shelter venue:* Pine Street Inn is a 470-bed shelter serving both men and women where BHCHP operates a medical clinic 7 days per week in the men's shelter and 6 days per week in the women's shelter.
- c) Day center venue:* St. Francis House is a multiservice day center for homeless people where BHCHP operates a medical clinic 5 days per week.

Study participants will be recruited through five methods:

- a) Self-referral:* Study staff will be stationed in heavily trafficked areas within the recruitment sites at prespecified times each week. We anticipate that a general awareness of the study due to study staff presence and word-of-mouth will encourage prospective participants to approach study staff and undergo eligibility screening if interested.

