### C. Treatment assignment

Participants will be randomized 1:1 to the control arm (n=90) or the financial incentives arm (n=90). Randomization will be stratified by housing status to ensure balanced representation of housed and homeless individuals across the 2 study arms. The attached Study Schema provides an integrated summary of the screening, enrollment, and randomization procedures along with the components of each study arm and the principal study outcomes.

The 2 study arms are as follows:

**1) Control arm (n=90):** Participants in this arm will be offered 12 weeks of varenicline and 5 sessions of tobacco coaching. As an attention control to help ensure a similar level of contact to the financial incentives arm, control arm participants will have the option to attend 10 cotinine monitoring visits over 12 weeks during which they would submit saliva samples for cotinine testing and receive a fixed debit card payment, irrespective of the result.

**2) Financial incentives arm (n=90):** Participants in this arm will be offered 12 weeks of varenicline and 5 sessions of tobacco coaching in a manner identical to the control arm. These participants will also have 10 cotinine monitoring visits over a 12-week period where they will receive debit card payments for saliva cotinine levels <30 ng/ml.

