### C. Statistical Methods

**Quantitative analysis:** Quantitative analysis will be based on the intention-to-treat principle. We will use Chi-squared tests to assess the difference between arms on attainment of the primary and secondary outcomes. Cochran-Mantel-Haenszel tests will determine whether the intervention effect is homogenous across study sites. We will use logistic regression to assess the intervention effect while adjusting for site. In primary analysis, participants who do not provide a saliva sample or are lost to follow-up will be assumed non-abstinent. A sensitivity analysis will use multiple imputation to impute missing outcomes data based on non-missing variables. In addition to cross-sectional analyses of the primary and secondary outcomes, we will conduct a repeated measures analysis of smoking status at 12 and 24 weeks to assess the overall impact of financial incentives on smoking abstinence. This analysis, which provides greater statistical power than cross-sectional analyses, will use generalized estimating equations (GEE) to account for the correlated data structure. We will also use GEE to analyze the other outcomes of changes in cigarette consumption, WHO ASSIST drug and alcohol scores, and mental health scores, each measured at baseline and 12 and 24 weeks.

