#### D. Power Analysis

Our power calculation is based on the Aim 1A outcome of cotinine-verified smoking abstinence at 12 weeks. With a sample arm of 90 per arm, we will have >80% power to detect a difference in abstinence at 12 weeks of 4% in the control arm and 17.5% in the incentives arm at a two-tailed p of 0.05.

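### The site-adjusted logistic regression names no estimator, test or sparse-data method, although the plan's own rates imply only about 3.6 control abstainers

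*Combined protocol and SAP*

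**What the plan says.** Statistical Methods (VI.C) compares the arms on the primary and secondary outcomes with unadjusted chi-squared tests. It then adds one sentence on the adjusted analysis: "We will use logistic regression to assess the intervention effect while adjusting for site". It does not state the estimator, the test statistic (Wald, likelihood-ratio or score), the interval method, or what happens when a cell is empty. Participants with a missing outcome count as non-abstinent, so all 90 per arm stay in the denominator. A sensitivity analysis uses multiple imputation.

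Power Analysis (VI.D) says "With a sample arm of 90 per arm, we will have >80% power" for abstinence of "4% in the control arm and 17.5% in the incentives arm", "at a two-tailed p of 0.05". Treatment assignment (IV.C) is 1:1.

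On sites, Source of subjects and recruitment methods (III.B) says: "Recruitment of study participants will occur at up to 3 venues; however, initial efforts will focus on the first of these sites". It gives no expected split between venues.

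**The concern.** This is the only model that the plan says adjusts for site, and its odds ratio and interval are likely to be reported beside the chi-squared result. With between three and four expected control events, the large-sample theory behind default maximum likelihood is weak. Three things can follow:

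- The odds ratio is biased away from 1.
- The Wald and likelihood-ratio tests from the same fit can disagree with each other and with the chi-squared test.
- The arm estimate does not exist if no control participant is abstinent.

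Because the plan fixes neither test nor fallback, those choices would be made after the data are seen. A second venue opened late could also be small, which adds sparse site terms to the model.

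**Working it through.** **Inputs.** 90 per arm, 4% vs 17.5%, two-sided 0.05 (VI.D); 1:1 allocation (IV.C); missing counted as non-abstinent (VI.C); up to three sites (III.B). Site splits, site effects and 24-week rates are not in the documents and are labelled as assumptions below.

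**1. The plan's own figure.** Difference 0.135. Null SE = sqrt(2 x 0.1075 x 0.8925 / 90) = 0.0462. Alternative SE = sqrt(0.04 x 0.96/90 + 0.175 x 0.825/90) = 0.0451. Power = Phi((0.135 - 1.96 x 0.0462)/0.0451) = 83.8%. Exact enumeration of all 91 x 91 outcomes gives 86.9% for the uncorrected chi-squared test. The stated power above 80% reproduces.

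**2. Event counts.** Control: 90 x 0.04 = 3.6. Incentives: 90 x 0.175 = 15.75. The probability of at most 3 control abstainers is 51%.

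**3. Odds ratio under maximum likelihood (two arms, same enumeration).** True value: (0.175/0.825)/(0.04/0.96) = 5.09. The geometric mean, given a finite estimate, is 5.51 (5.51/5.09 = 1.08). The median, ranking the infinite estimates highest, is 5.34 (5.34/5.09 = 1.05). Firth's estimate, which in the two-arm case amounts to adding 0.5 to each cell, has geometric mean 5.10 and is always finite.

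**4. No finite arm estimate.** P(no control abstainers) = 0.96^90 = 2.5%. If the 24-week control rate were 3% or 2% (assumption), 0.97^90 = 6% and 0.98^90 = 16%.

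**5. Tests (exact enumeration).**

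| Test | Power, 4% vs 17.5% | Rejection, 4% in both arms |
|---|---|---|
| Pearson chi-squared | 86.9% | 4.3% |
| Logistic, Wald | 82.0% | 0.9% |
| Logistic, likelihood-ratio | 87.1% | 7.6% |
| Firth, Wald | 82.8% | 0.8% |
| Firth, penalised likelihood-ratio | 86.9% | 3.3% |

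An undefined Wald test is counted as not significant. The Wald gap is 86.9 - 82.0 = 4.9 points. Of this, 2.5 points are the trials with no control abstainer from step 4, leaving 2.4 points in borderline trials.

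One such borderline result is 3 vs 10 abstainers. Chi-squared = (7/90)^2 / (0.0722 x 0.9278 x 2/90) = 4.06, p = 0.044. The log odds ratio is ln(10/80) - ln(3/87) = 1.288, with SE = sqrt(1/3 + 1/87 + 1/10 + 1/80) = 0.676, so the Wald z = 1.90, p = 0.057.

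**6. With site terms (4,000 simulated trials per scenario; splits assumed).** For splits of 34/33/33, 80/10/10 and 90/5/5 with no site effect:

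- Wald power is 80.8-81.9% against 85.8-86.9% for chi-squared.
- The geometric-mean maximum-likelihood odds ratio is 5.56-5.66, and the median 5.28-5.34.
- Firth's geometric mean is 5.06-5.14.

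With a 60/20/20 split and site effects of +/-0.5 log-odds, the Wald gap is 3.3 points. Some coefficient is infinite in 3%, 27% and 62% of trials for the three splits in order. The arm coefficient itself is infinite in only about 2.5%. The penalised likelihood-ratio figures in step 5 come from the two-arm enumeration only.

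**7. Sensitivity to the control rate.** At 8% vs 21.5% (same 13.5-point difference) the gap between Wald and chi-squared falls to 1.6 points, and P(no control abstainers) = 0.92^90 = 0.06%.

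**The case against.** The strongest reply is that nothing the plan promises is lost. The arms are compared by chi-squared, the power statement rests on that test, and even the Wald test stays just above 80%. A reader might infer that the trial gives up about 5 points of power. The documents do not support that, because the gap belongs to a separate adjusted model and appears only if that model is read from a Wald test, which the plan never names. Nor are the power gap and the non-finite estimate two separate harms, since about half of the gap is the zero-control-event trials. All of this stands.

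A reader might also infer that a small venue with no abstainers would break the analysis. It would not: that site's own coefficient is infinite, but the arm odds ratio stays finite. If only one venue recruits, there is no site term at all.

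The bias is also small against sampling error. At expected counts the SE of the log odds ratio is sqrt(1/3.6 + 1/86.4 + 1/15.75 + 1/74.25) = 0.61. The 95% interval is therefore about 1.6 to 16.7, and moving from 5.5 to 5.1 inside it changes no conclusion. The 4% is itself only a planning assumption. The pilot control arm had 8% at 8 weeks, on a looser, breath-based criterion (I.B).

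The objection does not remove the missing specification. Pointing to the likelihood-ratio test as the cure for Wald's conservatism replaces a test that rejects 0.9% of the time with one that rejects 7.6%. With neither test fixed in advance, the adjusted p-value depends on an open choice.

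**Conclusion.** The concern holds as a gap in the adjusted analysis, not as a flaw in the primary test or the sample size. At the plan's rates, default maximum likelihood inflates the odds ratio by about 8% (geometric mean, given a finite estimate) or 5% (median), gives no finite arm estimate in 2.5% of trials, and offers two standard tests that miss 5% on opposite sides. It goes beyond missing detail because a concrete better method exists: Firth with penalised likelihood-ratio inference has 86.9% power and 3.3% null rejection, and always gives a finite estimate.

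These sizes rest on the 4% control rate and on reading an unqualified reference to logistic regression as maximum likelihood. The problem shrinks at higher control rates and grows if 24-week abstinence is lower, for which the documents give no figure. With one recruiting site, the sparse control arm, the bias and the zero-event case remain.

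**What to change.** In VI.C, state that the site-adjusted models for the 12- and 24-week outcomes are fitted by Firth penalised logistic regression, with penalised likelihood-ratio p-values and profile-likelihood confidence intervals. Name the test explicitly, because a Firth fit read from a Wald test has only 82.8% power and recovers little of the gap. Beside each chi-squared test, report the risk difference with a Newcombe or Miettinen-Nurminen interval, which stays defined when an arm has no events.

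The cost is SAP wording and a modest amount of analysis work, with no change to design, sample size or conduct. The reported odds ratio will be slightly smaller. If the adjusted model is also fitted in the multiple-imputation sensitivity analysis, the SAP must say how penalised-likelihood tests and profile intervals are pooled across imputations.

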Mental/physical health	General health status (SF-1); single item measurement of cigarette craving; chronic medical conditions; Domains related to COVID-19, including diagnosis and symptom history, change in quitting motivation, and receipt of the COVID-19 vaccine; AUDIT, DAST-10; past 3-month drug use inventory; PHQ-9; GAD-7; MDQ; PSQ
Tobacco use	Age of initiation; past quit attempts (<math>\geq 24</math> hours) ; use of cessation aids; use of e-cigarettes or vape products; cigarettes/day ; Fagerstrom Test for Nicotine Dependence  ; 10-point importance and confidence scales ; stage of change ; Contemplation Ladder ; social support for quitting  ; past month use of alternative tobacco products 

**3) On-treatment monitoring visit data elements:** The following variables will be collected at the timepoints specified in parentheses. If participants miss their week 12 monitoring visit, the underlined elements will be asked during the follow-up survey visit up to 2 weeks later.

- Point-of-care saliva cotinine level (every monitoring visit, per Figure 3)
- Date and time last smoked all or most of a cigarette (every monitoring visit)
- Date and time of last puff of cigarette (every monitoring visit)
- Number of smoking days in the past 7 days (every monitoring visit)
- Average number of cigarettes per day (every monitoring visit)
- Use of vape or e-cigarette in past 7 days (every monitoring visit)
- Use of other tobacco products in past 7 days (every monitoring visit)
- Single item measurement on cigarette craving (every monitoring visit)
- Past week use of varenicline prescribed by study clinician (every monitoring visit)
- Average number of varenicline pills taken per day (if applicable, based on whether the participant is prescribed varenicline by the study clinician; every monitoring visit)
- Use of other quit smoking aids (every monitoring visit)
- Side effects to varenicline, including abnormal dreams, aggressive/erratic behavior, headaches, nausea, sleep disturbance/insomnia, vomiting, and other (if applicable; every monitoring visit)

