## B. Study Endpoints

**1) Primary outcome:** The Aim 1A outcome is saliva cotinine-verified 7-day smoking abstinence at 12 weeks. Participants who report not smoking in the past 7 days and have a saliva cotinine level of <10 ng/mL at the week 12 timepoint will be considered abstinent.

**2) Secondary outcome:** The Aim 1B outcome is 7-day smoking abstinence at 24 weeks, based on self-report and verified by a salivary cotinine level of <10 ng/mL.

**3) Other outcomes:** Other outcomes include 7-day smoking abstinence at weeks 1-11 (defined as no smoking the past 7 days and having a point-of-care saliva cotinine level <30 ng/ml), use of varenicline or other smoking cessation medications (assessed by self-report and BHCHP chart review), use of other tobacco treatment resources, changes in past-month drug and alcohol use and psychiatric symptoms (assessed with the AUDIT, DAST-10, drug use inventory, PHQ-9, GAD-7, at 12 and 24 weeks).

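### The adjusted logistic model includes site, which randomization was not stratified by, but omits housing status, which it was, and any prognostic baseline value; adding housing status and the baseline Fagerstrom score is a low-cost refinement with a small expected gain

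*Combined protocol and SAP*

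**What the plan says.** Section VI.C takes the main comparison from unadjusted tests: "We will use Chi-squared tests to assess the difference between arms on attainment of the primary and secondary outcomes". It then adds one adjusted cross-sectional model: "We will use logistic regression to assess the intervention effect while adjusting for site". No other covariate is named for an abstinence model in that section.

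Four other places bear on this sentence.

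- **Stratification.** Sections IV.A and IV.C stratify the 1:1 randomization by housing status, not by site.
- **Sites.** Section II speaks of three recruitment sites. Section III.B allows up to three, begins with the medical center venue, and makes the other two depend on the course of the pandemic.
- **Baseline data.** The baseline survey in Section VI.A includes the "Fagerstrom Test for Nicotine Dependence". Section V.A places that survey at the enrollment visit, before randomization.
- **Restarted participants.** Under Section V.H, the 11 people enrolled before the pause may restart. They repeat the survey, those already randomized keep their assignment, and the latest data are the ones analysed.

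The power statement in Section VI.D is a plain two-proportion comparison and relies on no covariate: "4% in the control arm and 17.5% in the incentives arm", with 90 per arm, "at a two-tailed p of 0.05".

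**The concern.** An adjusted analysis normally conditions on the factors used to stratify the randomization and on one or two strong baseline predictors of the outcome. The planned model does neither. If recruitment stays at one venue, the site term is constant and the model adds nothing to the unadjusted comparison.

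Dependence is a plausible predictor of quitting on the protocol's own account: Section I.A mentions heavier smoking and higher dependence while discussing why few homeless smokers succeed. Including it would protect the adjusted estimate against chance imbalance and might add some power. Naming the covariate now also removes later discretion over which one to use.

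**Working it through.** **1. The plan's own figure.** Inputs from Section VI.D: n = 90 per arm, 4% versus 17.5%, two-sided 0.05.

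- Mean rate = (0.04 + 0.175)/2 = 0.1075.
- Null SE = √(2 × 0.1075 × 0.8925 / 90) = 0.04618.
- Alternative SE = √((0.04 × 0.96 + 0.175 × 0.825) / 90) = 0.04507.
- Power = Φ((0.135 − 1.96 × 0.04618) / 0.04507) = Φ(0.987) = 83.8%.

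Exact enumeration gives 86.9% for the uncorrected chi-squared test and 81.7% for Fisher's test. Only the Yates-corrected test falls below 80%, at 79.2%. The claim of more than 80% reproduces without any covariate.

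**2. Events available.** 90 × 0.04 + 90 × 0.175 = 3.6 + 15.75 = 19.35 expected abstinent participants.

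- Arm, housing status and Fagerstrom score: 3 terms, 19.35/3 ≈ 6.5 events per term.
- Arm, two site terms and two baseline covariates: 5 terms, 19.35/5 ≈ 3.9 events per term.

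**3. Power with one covariate.** Simulation: 4,000 trials per setting, 90 per arm, one standard-normal covariate, Pearson test against the score test for arm in the adjusted logistic model. The documents do not say how strongly dependence predicts cotinine-verified abstinence, so the odds ratio (OR) per SD is an assumption and is shown as a range. The second pair of rates is a what-if, not the plan's.

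| OR per SD | 4% vs 17.5%: Pearson → adjusted | 8% vs 21.5%: Pearson → adjusted |
|---|---|---|
| 1.0 | 86.4% → 86.6% | 74.5% → 74.6% |
| 0.7 | 86.6% → 86.8% | 73.7% → 74.5% |
| 0.5 | 86.2% → 87.8% | 73.9% → 76.4% |
| 0.3 | 87.3% → 90.7% | 73.8% → 80.3% |

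The Monte Carlo SE of one entry is √(0.87 × 0.13/4000) ≈ 0.5 point on the left and √(0.74 × 0.26/4000) ≈ 0.7 point on the right. A run of 8,000 trials at 4% versus 17.5% gave gains of 0.0, 0.1, 0.7 and 3.5 points at ORs 1.0, 0.7, 0.5 and 0.3. A run that also fitted housing status gave about 0 at ORs 1.0 to 0.7, 1 at 0.5 and 3 at 0.3. An OR of 0.5 corresponds to a covariate AUC of about 0.68, and 0.3 to about 0.77.

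**4. Type I error.** The score test stayed at 4.6% to 5.5% across runs. The likelihood-ratio test reached 6% to 8% when both arms had a 4% rate, so the choice of test matters with so few events.

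**5. Precision of the risk difference.** A separate simulation used two covariates with correlation 0.5. The ratio of adjusted to unadjusted variance was 1.011, 1.001, 0.985 and 0.962 for ORs of 1.0, 1.2, 1.35 and 1.5 per SD, and 0.885 at 2.0. In patient terms, 180 behave like 180/0.962 ≈ 187 at OR 1.5 and 180/0.885 ≈ 203 at OR 2.0.

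**6. Housing status.** The documents give neither the share of participants housed nor its relation to abstinence, so no separate gain can be computed. The case for including it is that the design balanced on it.

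**The case against.** **The main test is unaffected.** The chi-squared test carries the primary and secondary outcomes, and it stays. A reader might infer that the trial as planned is underpowered or loses precision in its main result. The documents do not support that: the stated power reproduces, and every gain above belongs to the adjusted model. Nor does logistic adjustment shrink the SE of the log odds ratio; it moves the estimate to a conditional odds ratio. The benefit appears as power of the adjusted test or as precision of a standardised risk difference.

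**The gain may be nil.** Prognostic strength is nowhere given. Section III.A admits only daily smokers of at least 5 cigarettes who are ready to try quitting within 3 months, which may narrow the spread of dependence. This stands.

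**The 8% scenario is not the plan's.** A reader might call 4% optimistic because the pilot's control arm reached 8%. That figure was exhaled CO below 8 ppm at 8 weeks with nicotine patches (Section I.B); the endpoint here is 7-day abstinence with cotinine below 10 ng/mL at 12 weeks (Section VI.B). The earlier large trial's 5.6% to 9.3% (Section I.A) was at 6 months. Neither shows that 4% is wrong.

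**Other analyses use baseline data.** Section III.A plans interaction analyses with drug and alcohol severity, and the multiple-imputation sensitivity analysis could draw on the Fagerstrom score. So baseline data are not ignored altogether, but neither analysis supplies the adjusted treatment effect discussed here.

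**Site may still matter.** Adjusting for a factor that was not stratified is not an error, and three venues remain possible. Site therefore need not be deleted. It should be conditional on more than one venue recruiting.

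**Few events.** About 19 events limit the model. They argue against also adding cigarettes per day, which is collected too, but do not rule out one continuous covariate with a suitable test.

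**Conclusion.** The point holds as a minor, optional improvement to one supportive analysis. The adjusted model names a factor that was not stratified and may be constant, and omits both the stratification factor and any prognostic baseline value.

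At the design rates the expected gain is about 0 to 1 point of power for ORs of 1.0 to 0.5 per SD, and about 3 points at 0.3. At 8% versus 21.5% it is about 0 to 2 points (2.5 at OR 0.5 in the tabulated run), and 6 to 7 points at 0.3. No measurable power is lost if the score is uninformative. These figures assume a roughly normal covariate with a log-linear effect, a score test, and a strength that the documents do not give. The primary result and its stated power do not change.

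**What to change.** Amend the logistic-regression sentence in Section VI.C so that it states the following:

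- The chi-squared test remains the main test, and the logistic model is supportive.
- The model contains arm, housing status as used at randomization, and one pre-specified covariate: the baseline Fagerstrom score as a continuous value.
- Site is added only if more than one venue recruits.
- The arm effect is tested with a score or penalised-likelihood test, because about 19 events are expected.
- A standardised risk difference is reported beside the odds ratio, since the conditional odds ratio is not comparable with the unadjusted one.
- For restarted participants, the score to be used is named. The latest-data rule in Section V.H would select a survey completed after assignment for anyone already randomized before the pause. This concerns at most 11 people.

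The cost is SAP wording, settled before outcome data are examined by arm. No extra participants, visits or data items are needed.

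### Section VI.C does not say how baseline enters the GEE for changes in cigarette, substance-use and mental health measures; run in either of two ordinary ways, it gives up precision that baseline adjustment would recover

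*Combined protocol and SAP*

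**What the plan says.** Section VI.C (Statistical Methods) gives one sentence to these analyses. It begins "We will also use GEE to analyze the other outcomes of changes in cigarette consumption" and continues with "WHO ASSIST drug and alcohol scores, and mental health scores, each measured at baseline and 12 and 24 weeks". Section VI.B, under other outcomes, likewise lists "changes in past-month drug and alcohol use and psychiatric symptoms".

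No response variable, mean model, covariate or working correlation is given for this GEE. The only covariate named in VI.C belongs to the abstinence analysis: "We will use logistic regression to assess the intervention effect while adjusting for site". Nothing says that baseline is adjusted for, or that the arms are given a common baseline mean.

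Section V.H also bears on the point. The 11 participants enrolled before the pause may restart. They repeat the baseline survey, those already randomised keep their original arm, and the latest data replace the earlier data in the analysis. The earlier data are archived.

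**The concern.** Two ordinary ways of carrying out the sentence are to regress follow-up minus baseline on arm, or to enter baseline, week 12 and week 24 as three response rows with a free arm-by-time term. Both estimate a difference in changes. Both carry the full baseline noise, and both let the arms differ at baseline although randomisation makes their expected baseline means equal. Conditioning on the baseline value targets the same arm contrast with smaller variance.

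What is at stake is the width of the confidence intervals. Section III.A treats drug and alcohol use as a potentially important issue in this population, and Section X.B relies on the absence of worsening in the pilot trial when it discusses misuse of payments. A statement that payments did not worsen drinking, drug use or symptoms is only as strong as the harm its interval excludes. Section VI.D gives no power for these outcomes.

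Chance imbalance matters too. Randomisation is stratified by housing status only, so nothing in the design balances baseline substance-use scores, symptom scores or cigarettes per day.

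**Working it through.** **The plan's own figure.** The only power statement is for 12-week abstinence: "With a sample arm of 90 per arm, we will have >80% power to detect a difference" of "4% in the control arm and 17.5% in the incentives arm at a two-tailed p of 0.05". With mean proportion 0.1075, z = [0.135 × √90 − 1.96 × √(2 × 0.1075 × 0.8925)] / √(0.04 × 0.96 + 0.175 × 0.825) = (1.281 − 0.859) / 0.428 = 0.987, a power of 83.8%. The figure reproduces, but it does not bear on the GEE outcomes.

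**Inputs.** From the documents: 90 per arm, and measurements at baseline, 12 and 24 weeks. Not in the documents, so assumed: the correlation r between baseline and follow-up (0.3 to 0.7) and the ratio k of follow-up SD to baseline SD (1, then 0.7 to 1.3).

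**Formulas** (linear model, complete data, one visit, baseline SD = 1):
- Variance of the change-score contrast is proportional to 1 + k² − 2rk.
- Variance of the baseline-adjusted contrast is proportional to k²(1 − r²).
- The difference is (1 − rk)², which is never negative. Adjustment is therefore never asymptotically worse, whatever r and k are.
- Fraction of precision lost = (1 − rk)² / (1 + k² − 2rk). With k = 1 this reduces to (1 − r)/2.

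**Precision lost at one visit:**

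| SD ratio k | r = 0.3 | r = 0.5 | r = 0.7 |
|---|---|---|---|
| 0.7 | 58% | 53.5% | 51% |
| 1.0 | 35% | 25% | 15% |
| 1.3 | 19.5% | 9% | 1% |

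With k = 1 the change-score standard error is larger by 24%, 15% and 8.5% at r = 0.3, 0.5 and 0.7. At r = 0.5 the loss equals 1/0.75 − 1, or about 33% more participants for the same precision.

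**Do the candidate models behave this way?** In 250 simulated complete-data trials of 180 per value of r (k = 1, exchangeable correlation):
- GEE on all three times with arm means free at baseline gave the same 12-week estimate as the change score, with differences below 1e-15.
- GEE with a common baseline mean had variance 0.64, 0.75 and 0.86 of the change-score variance at r = 0.3, 0.5 and 0.7.
- Baseline adjustment gave 0.65, 0.76 and 0.87, against 0.65, 0.75 and 0.85 from the formula.

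So listing baseline as a measurement time does not by itself recover the precision. A baseline covariate does, and so does a common baseline mean.

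**Chance imbalance.** With 90 per arm, one standard error of the baseline difference is √(2/90) = 0.149 SD. Given that imbalance, a change-score contrast shifts by (1 − r) × 0.149 = 0.075 SD in size at r = 0.5 and k = 1. Adjustment removes this shift.

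**Restarted participants.** At most 11 of 180 (6.1%) could have an analysed baseline taken after assignment. For them randomisation does not guarantee equal baseline means between the arms.

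**The case against.** The strongest objection is that the plan does not state a change-score model. The word changes may only label the outcome, and "each measured at baseline and 12 and 24 weeks" fits a GEE with baseline in the response vector and a common baseline mean. Under that reading essentially nothing is lost. This stands: a reader might infer that the plan commits to an unadjusted change score and so discards 15% to 35% of the precision, but the text supports neither step. The model is unstated, and that range is (1 − r)/2 at assumed correlations with equal SDs. Equal SDs are doubtful for cigarettes per day, since entry requires at least 5 per day and quitters move to zero.

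It is also fair to say that these are other outcomes. The trial's hypotheses concern abstinence, no margin or formal no-harm test depends on these intervals, and psychiatric safety is also followed by suicidality screening, side-effect checklists, adverse event reporting and the DSMB. That limits the importance of the point.

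It does not remove it. Two ordinary readings give the same less precise contrast, the text does not exclude them, and the better analysis uses data already collected.

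**Conclusion.** The point holds conditionally. Section VI.C leaves the role of baseline open. If these outcomes are analysed as change scores, or with arm means free at baseline, each visit's contrast loses (1 − r)/2 of the attainable precision when SDs are equal, for example 15% to 35% for r from 0.7 down to 0.3. Over the same r with SD ratios of 0.7 to 1.3 the loss is about 1% to 58%. The direction is general for linear complete-data models; the size rests on assumed r and SDs. Skewed scores and missing visits would alter the figures.

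A reader might also infer that the results would be biased or that the main conclusions are at risk. Neither follows. With randomised arms the change-score contrast is unbiased over repeated randomisation, so the cost is efficiency and sensitivity to chance imbalance. The primary and secondary abstinence tests do not use this model.

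**What to change.** In VI.C, state that the 12- and 24-week values of each measure will be modelled by GEE on arm, visit, arm by visit and the participant's baseline value of the same measure, and that the adjusted difference with its confidence interval will be reported at each visit.

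Add a sentence for already randomised participants who restart. Either use their archived pre-randomisation baseline as the covariate, which needs an exception to the rule in V.H that earlier data are disregarded, or repeat the analysis without them as a sensitivity check. An equal-baseline-means constraint should not be relied on for these participants.

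The cost is a few lines of SAP text. Baseline values are already collected at enrolment, and no participants, visits or measurements are added. Fixing the model in advance also removes the choice among models after the data are seen.
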